7.3 End-of-treatment visit

Unless a patient withdraws consent for trial participation, or is lost to follow-up, an End-of-Treatment Visit should be performed as soon as possible (no later than 30 days) after the treatment

has been discontinued. Every effort should be made to conduct the End-of-Treatment Visit before the patient starts subsequent therapy. If a patient is unable to return to the site for the End-of-Treatment Visit, then the patient should be contacted (e.g., by phone) to collect information on AEs and concomitant therapies and other EOT visit assessments (in particular PROs) to the extent possible that occurred within 30 days after the last treatment. Additional information on reporting of AEs can be found in Section 8.8.4.1.

Patients who permanently discontinue treatment at some point after the administration of the first dose of trial medication will not be replaced.

8 Trial assessments and procedures

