9.2 Sample size determination

Sixty two (62) patients will be screened. 33 patients will be randomised in a 1:1 ratio of MC2-25 cream to MC2-25 vehicle. For a two-sided test with a 5% level of significance and an effect size of 1 standard deviation, this sample size will provide adequate power ($\geq 78\%$) to compare mean change in mean weekly WI-NRS from Baseline to Week 12 between MC2-25 cream and MC2-25 vehicle with 16 to 17 patients per treatment group.

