## 2.4 Study Endpoints

### 2.4.1 Efficacy

The primary endpoint is the mean change in weekly mean Worst Itch Numeric Rating Score (WI-NRS) recorded in the patient's diary from Baseline to Week 12 for *MC2-25 cream* compared to *MC2-25 vehicle*.

(Weekly mean WI-NRS is calculated as the average of WI-NRS values recorded in the patient's diary for 7 days prior to the in-clinic visits).

The secondary endpoints (all defined from Baseline to Week 12 for MC2-25 cream compared to MC2-25 vehicle) are:

- Mean change in weekly mean Worst Pain Numeric Rating Score (WP-NRS) recorded in the patient's diary (Weekly mean WP-NRS is calculated as the average of WP-NRS values recorded in the patient's diary for 7 days prior to the in-clinic visits.)
- Percentage of patients obtaining a  $\geq 4$ -point improvement in weekly mean WI-NRS recorded in the patient's diary
- Percentage of patients obtaining a  $\geq 4$ -point improvement in weekly mean WP-NRS recorded in the patient's diary
- Percentage of patients obtaining a  $\geq 3$ -point improvement in weekly mean WI-NRS recorded in the patient's diary
- Percentage of patients obtaining a  $\geq 3$ -point improvement in weekly mean WP-NRS recorded in the patient's diary
- Change in Skindex-29 domains

Primary and secondary endpoints will be confirmatorily analyzed as described in Sections 5.2 to 5.5. Other endpoints will be exploratorily analyzed.

Other endpoints (all defined from Baseline to Week 12) include:

- Percentage of patients obtaining a complete response (score  $\leq 1$ ) in weekly mean WI-NRS recorded in the patient's diary
- Percentage of patients obtaining a complete response (score  $\leq 1$ ) in weekly mean WP-NRS recorded in the patient's diary
- Mean change in Worst Itch Numeric Rating Score (WI-NRS) recorded at in-clinic visits
- Mean change in Worst Pain Numeric Rating Score (WP-NRS) recorded at in-clinic visits
- Mean change in Worst Penetrative sex related Pain Numeric Rating Score (WPP-NRS) recorded at in-clinic visits
- Percentage of patients obtaining a  $\geq 3$ -point improvement in WI-NRS recorded at in-clinic visits
- Percentage of patients obtaining a  $\geq 3$ -point improvement in WP-NRS recorded at in-clinic visits
- Percentage of patients obtaining a  $\geq 3$ -point improvement in WPP-NRS recorded at in-clinic visits

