**Patient reported outcomes (PRO) assessments****Worst Itch Numeric Rating Score (WI-NRS) of VLS**

The patient's WI-NRS score must be recorded by the patient in a diary once daily (i.e., every day around the same timepoint, e.g. morning, afternoon or evening) for a total of 7 days (i.e. starting 7 days before the next in-clinic visit and ending on the day before the next in-clinic visit) leading up to each in-clinic visit day at Baseline, Week 1, Week 4, Week 8, and Week 12 or End of Treatment (EoT) using an 11-point numeric rating scale ranging from 0 to 10:

*Please score the intensity of the Worst Itch associated with your lichen sclerosus, that you have experienced in the past 24 hours: 0 (no itch), 1, 2, 3, 4, 5, 6, 7, 8, 9, 10 (worst imaginable itch).*

In addition, the patient's WI-NRS score must be reported to the clinical staff at in-clinic visits at Screening 1, Baseline, Week 1, Week 4, Week 8, and Week 12 (or EoT) using the 11-point numeric rating scale above.

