#### Multiple Imputation

Post-baseline missing or invalid data will be multiply imputed within treatment groups in two steps [10]. At first, any potential intermediate missing data will be imputed 20 times using a Markov Chain Monte Carlo (MCMC) method to obtain a monotone missing data pattern. In a second step, imputation is done using a monotone regression method, fitting an analysis of covariance (ANCOVA) model stepwise visit by visit. The ANCOVA model adjusts for the effects of menopausal status at baseline, ICIQ-UI-SF score at baseline as factors, and the baseline value of the respective endpoint as a covariate. For each treatment group and each copy of the dataset, the estimated parameters and their variances are used to impute the endpoint. Starting with Week 1, the procedure is repeated on Week 4, Week 8 and Week 12, adding the possibly imputed values of the previous visits as covariates. On MI, missing score data is handled like missing continuous data.

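### The primary multiple imputation leaves out the in-clinic itch score from the same visit, so a woman who attends without diary data is imputed only from baseline covariates and her earlier weekly means

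*SAP*

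**What the plan says.** The primary endpoint is a diary variable. SAP 2.4.1: "Weekly mean WI-NRS is calculated as the average of WI-NRS values recorded in the patient's diary for 7 days prior to the in-clinic visits". The primary analysis is treatment policy on the FAS with multiple imputation (SAP 5.3 and 5.5.1). Protocol 9.4.2.1 assumes missingness at random and fixes 20 imputations and Rubin's rule, but names no imputation predictors.

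SAP 4.7.2 imputes within treatment group in two steps. MCMC fills intermediate gaps only; its predictors are not listed. A regression step then goes visit by visit, using menopausal status, ICIQ-UI-SF and the endpoint's baseline value, and "adding the possibly imputed values of the previous visits as covariates". No other predictor is named. Week 12 is the last visit, so a missing Week 12 value is never an intermediate gap and is always filled by the regression step.

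Separately from the diary, SAP 2.4.1 says the "WI-NRS score must be reported to the clinical staff at in-clinic visits at Screening 1, Baseline, Week 1, Week 4, Week 8", and the list continues to Week 12 or EoT. Protocol 1.3 (footnote 8) and 8.5.2.1 make this mandatory. SAP 5.5.3 gives the in-clinic score summary tables only. For a woman who stops treatment and cannot attend, Protocol 7.3 still seeks "other EOT visit assessments (in particular PROs) to the extent possible", by phone for example.

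**The concern.** The diary is kept only in the seven days before an in-clinic visit (Protocol 1.3, footnote 9). An unplanned end-of-treatment visit can therefore yield an in-clinic score with no diary week. SAP 4.6.2 takes unscheduled EoT visits into account, so one on study days 71-91 can serve as the Week 12 visit. Protocol 7.1 names lack of treatment effect as a reason for stopping, so such gaps may be related to itch.

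If these women itch more than their earlier diaries predict, the planned model draws their Week 12 values too low and the between-arm difference is biased. An observed variable that carries information on exactly this departure is left unused, which makes missing-at-random harder to defend. Nothing else in the SAP covers the gap. The four sensitivity analyses in SAP 5.5.1 are all unimputed, none uses the in-clinic score, and none takes up the missing-not-at-random option that Protocol 9.4.2.1 leaves open.

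**Working it through.** **1. The plan's own figure.** Protocol 9.2: "For a two-sided test with a 5% level of significance and an effect size of 1 standard deviation", "this sample size will provide adequate power" (78% or more) "with 16 to 17 patients per treatment group". A two-sample t-test has noncentrality 1/sqrt(1/n1 + 1/n2). For 16 and 17 this is 2.87 with 31 degrees of freedom, giving 79.4%; for 16 and 16 it gives 78.1%. The stated power reproduces. Nothing below changes it, but it leaves little margin for attenuation.

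**2. What the in-clinic score could add.** The documents give no correlations, so these are assumed. Diary means at any two visits correlate rho = 0.4, 0.6 or 0.8. The same-visit in-clinic score correlates r = 0.6 to 0.9 with the diary mean, its error being independent of history.

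- R-squared for Week 12 from the four earlier diary means (baseline, Weeks 1, 4, 8) = 4 rho² / (1 + 3 rho): 0.64/2.2 = 0.29, 1.44/2.8 = 0.51, 2.56/3.4 = 0.75.
- With v = 1 - R-squared, the share of a woman's departure from her predicted value that the in-clinic score recovers = r²v / (r²v + 1 - r²).
- Results for r from 0.6 to 0.9: 28-75% (rho 0.4), 21-67% (rho 0.6), 12-51% (rho 0.8).

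**3. Size of the bias.** If k of 16 women in one arm lack the Week 12 diary and are d SD worse than their history predicts, the arm mean is off by k × d / 16 SD. For d = 1: 0.06 SD (k = 1), 0.125 (k = 2), 0.19 (k = 3), 0.25 (k = 4). For d = 0.5 these halve. The design effect is 1 SD, so the same numbers are the fraction of the effect lost.

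**4. Simulation with selective missingness.** Assumed: 17 cream and 16 vehicle women, SD 2, true difference -2.0, three vehicle women without a Week 12 diary but with an in-clinic score, and Week 12 ANCOVA in place of the MMRM.

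- *The three with the worst in-clinic score* (r = 0.7 or 0.85). Planned model: -1.58 to -1.64 at rho 0.4, -1.72 to -1.76 at 0.6, -1.84 to -1.89 at 0.8. With the score added: -1.99 to -2.03 throughout.
- *The three with the worst weekly mean* (rho 0.6). At r = 0.7 the planned model gives -1.66 and adding the score -1.75, so 0.09/0.34, about 26%, of the bias is removed. At r = 0.85 it gives -1.64 and -1.83, so 0.19/0.36, about 53%.
- Over the settings examined under both mechanisms, the planned model attenuates by about 7-27%; under weekly-mean selection the score removes about 13-57%. The limits are approximate: the mildest setting in the first bullet, -1.89, is a 5.5% attenuation.

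**5. Random missingness.** Both models are unbiased. With one, two or three women per arm missing, one set of runs gave power changes of +0.7, +1.9 and +5.5 points at r = 0.85, and between -0.6 and +0.8 at r = 0.7. A wider set, fitted within arm, gave about -3 to +15 points.

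**6. Model size.** Within one arm the Week 12 model has seven coefficients (intercept, menopausal status, linear ICIQ-UI-SF, baseline, three visits), and more if ICIQ-UI-SF is a factor, as SAP 4.7.2 words it. With 13 of 16 women observed, 13 - 7 = 6 residual degrees of freedom remain, or 5 with one more predictor. With three missing in one arm, adding the score within arm sometimes raised the SD of the estimate slightly (0.66 to 0.69); a model pooled over arms with a treatment term gave 0.62.

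**The case against.** No rule is broken. Imputing from baseline covariates and all earlier visits is a legitimate missing-at-random model, and auxiliary variables are optional. That stands: this is a missed improvement, not an error or a contradiction.

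The case may be rare. No post-baseline minimum of diary days is stated; the four-score minimum in Protocol 5.1 applies to Baseline. Read literally, a single entry gives a weekly mean, so the gap needs a woman who attends with no entries. Diary reminders are scheduled and diaries are checked while she is in clinic (Protocol 1.3, footnotes 4 and 10). An EoT score from, say, Week 5 is not a Week 12 measure, and a woman with no Week 12 visit usually has no score either. All of this stands, and the frequency is unknown.

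The simulated scenario is also severe: three of 16 missing in one arm, none in the other, all from the worst. A bias of 0.18-0.24 points, as in some settings, is under half a standard error of about 0.6, and here it runs towards no effect.

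A reader might infer two stronger things. One is that nothing is known about such a woman's itch. In fact her baseline and any Week 1, 4 and 8 diary means are used; only the current visit is ignored. The other is that the in-clinic score largely removes the bias. That follows only when missingness is driven by the in-clinic score itself, the very variable then added. When it is driven by the weekly mean, about half or more of the bias usually remains.

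**Conclusion.** The point holds as a specific, inexpensive improvement to the primary imputation. The omission is clear from the text: a mandatory same-visit measure of the same item is absent from the stated predictors and from every sensitivity analysis.

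Its size is conditional. With three of 16 vehicle women missing selectively, the planned model loses about 7-27% of a true -2.0 difference. The in-clinic score recovers nearly all of that or about 13-57%, depending on what drives the missingness. If no woman attends without diary data, or her in-clinic score is missing too, it recovers nothing. These figures rest on assumed correlations and a Week 12 ANCOVA rather than the planned MMRM. In the simulations behind the 7-27% and 13-57% ranges, adding the score did not raise the root mean squared error in any setting, although within-arm precision can worsen slightly. The documents do not support saying that the primary result will be biased, or that the change would make it unbiased.

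**What to change.** Before unblinding, amend SAP 4.7.2 and list the change in SAP 5.6:

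- Add the same-visit in-clinic WI-NRS as an auxiliary predictor of the weekly mean WI-NRS, and the in-clinic WP-NRS for the WP-NRS endpoint. It is one 24-hour recall, so it must not replace the seven-day mean.
- Match it to the diary week by the analysis windows of SAP 4.6.2. That section otherwise handles in-clinic scores by nominal visit.
- Place it immediately before that visit's diary mean in the monotone sequence, so that it is itself imputed when missing. Let only the same-visit score enter each diary model, and name the predictors of the MCMC step.
- Enter ICIQ-UI-SF as linear. Pre-specify a model pooled over arms with a treatment term as the fallback if the within-arm model is not stable.
- State the post-baseline minimum of diary days, so that it is clear when a weekly mean counts as missing.

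The endpoint, estimand and MMRM stay as they are, and no new data are needed. The cost is a short SAP paragraph, somewhat more complex imputation code, and one more coefficient per visit in a model fitted to 16-17 women per arm.

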#### Worst-case Imputation

For the secondary endpoints with 3- and 4-point improvements in weekly mean WI-NRS and WP-NRS from the patient's diary, a *worst-case imputation* will be employed, where no improvement will be assumed for any missing endpoints.

## 5 Statistical Methods

### 5.1 Conventions for Inference

The two-sided level of significance is set to  $\alpha = 0.05$ , the one-sided level of significance to  $\alpha = 0.025$ .

## 5.2 Statistical Hypotheses

Let  $\mu_M$  and  $\mu_V$  be estimators of treatment effect for each endpoint for MC2-25 cream, and MC2-25 vehicle. The following statistical hypothesis will be tested.

$$H_0: \mu_M = \mu_V \text{ versus } H_1: \mu_M \neq \mu_V$$

Statistical significance will be tested at the two-sided 5% significance level unless otherwise specified. Superiority is concluded if a p-value of statistical hypothesis testing is below the significance level and the estimate of treatment difference is in a favourable direction for MC2-25 cream. Estimates of treatment effects and differences from baseline at time points other than Week 12 will be reported exploratively.

## 5.3 Multiplicity Adjustment and Estimands

No multiple testing adjustment will be employed in this study.

The primary endpoint will be analyzed by different estimands, following a treatment policy strategy with imputation (primary estimand) (Section 4.7.2), a treatment policy strategy without imputation (secondary estimand), and a while on treatment strategy without imputation (tertiary estimand).

For the primary estimand, all available data will be used, regardless of treatment and treatment adherence, with missing data imputed as described in Section 4.7.2. For the secondary estimand, all available data will be used, regardless of treatment and treatment adherence, and missing data will not be imputed.

For the tertiary estimand, all available data will be included up to 7 days after the last treatment intake, regardless of treatment and treatment adherence, and missing data will not be imputed. Data more than 7 days after the last treatment intake is invalid and will not be used.

## 5.4 Approaches for Analysis

All collected, recorded, and derived data for analysis will be listed in individual patient data listings for all randomised patients. For both WI-NRS and WP-NRS, 4- and 3-point improvements, as well as complete response (score  $\leq 1$ ) will be flagged in listings; for WPP-NRS, a 3-point improvement will be flagged in a listing. For PGIC in Worst Itch (WI), Worst Pain (WP) and Worst Penetrative sex related Pain (WPP), as well as CGIC, an improvement ('Very much better', 'Much better' or 'A little better') will be flagged in listings. For CGA of VLS, a  $\geq 2$ -point improvement will be flagged in a listing.

### 5.4.1 Binary Data

The binary secondary endpoints (Section 2.4.1) will be analysed using a logistic model with effects of treatment, menopausal status at baseline, ICIQ-UI-SF score at baseline, and the baseline value for each scale the binary endpoint is derived from (WI-NRS or WP-NRS) as factors. The estimated log odds ratios between the treatments at Week 12 will be derived together with the associated standard error and 95% confidence intervals. These binary endpoints will be summarized in descriptive tables and visualized in bar charts, in both cases stratified by treatment group and visit.

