5.1 Inclusion criteria

Participants must meet all the following criteria to be eligible for participation in the trial:

1. Women, of any race or ethnicity, who are ≥ 18 years of age at the time of Screening 1.
2. Able to understand the trial and willing to comply with trial requirements.
3. Has provided written informed consent.
4. Clinical diagnosis of VLS (i.e., biopsy for histological confirmation not required except if needed to rule out malignancy or differential diagnosis of e.g., vulvar lichen planus) made by either a dermatologist or a gynaecologist familiar with VLS.
5. Presence of at least one of the following signs of VLS: a. Hyperkeratosis (i.e., patches/plaques of bright white skin with a 'powdery' texture) and/or b. Sclerosis (i.e., areas of yellowish/ivory white skin with a smooth/waxy/firm texture. Sclerosis is often seen at the tips of the labia minora, or on periclitoral or perineal skin) in at least one of the following vulvar areas: Clitoris and/or periclitoral skin (C); Right interlabial sulcus and labium minus (R); Left interlabial sulcus and labium minus (L); Posterior Fourchette and/or perineum (P) (see protocol section 8.5.1.2).
6. First symptoms of VLS (e.g., itching and/or pain) noticed by the patient at least 6 months before baseline.
7. At least four WI-NRS scores available in the diary for calculation of the average WI-NRS at the baseline visit.
8. At least moderate itch defined as average WI-NRS ≥ 4 at the Baseline visit (average WI-NRS is calculated as the average of all available and at least four WI-NRS scores which are to be reported once daily by the patient in the diary for 7 days prior to the Baseline visit (7 days in total)).
9. Women must be of either:
 - a) Non-childbearing potential, i.e., post-menopausal* or confirmed sterile (e.g., hysterectomy, bilateral salpingectomy or bilateral oophorectomy) (*Note: a postmenopausal state is defined as no menses for 12 months without an alternative medical cause. A high follicle stimulating hormone (FSH) level in the postmenopausal range may be used to confirm a postmenopausal state in women not using hormonal contraception or hormonal replacement therapy. However, in the absence of 12 months of amenorrhea, a single FSH measurement is insufficient) OR,

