9.4.2.2 Analysis of the secondary endpoints

Secondary endpoints include mean changes in weekly mean WP-NRS and in Skindex-29 domain scores as well as percentages of participants obtaining a ≥ 3 -point or a ≥ 4 -point improvement in weekly mean WI-NRS and weekly mean WP-NRS, respectively.

Mean changes in weekly mean WP-NRS and in Skindex-29 domain scores on the FAS will be analysed as described in Section 9.4.2.1 for primary and sensitivity analyses on mean changes in weekly mean WI-NRS. On the FAS, percentages of participants obtaining a ≥ 3 -point or a ≥ 4 -point improvement in weekly mean WI-NRS and weekly mean WP-NRS will be analysed by means of logistic regression adjusting for respective NRS scores at baseline. If the endpoint is missing, no improvement is assumed.

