### 4.3 Subgroups and Confounding Factors for Analysis

The mixed model for repeated measures (MMRM) for continuous endpoints (primary and secondary) will be adjusted by menopausal status at baseline, ICIQ-UI-SF score at baseline, and the respective baseline

value of the endpoint being modelled. Similarly for the two binary secondary endpoints, which will be analyzed using a logistic regression at Week 12, the models will be adjusted by menopausal status at baseline, ICIQ-UI-SF score at baseline, and the baseline value for each scale the binary endpoint is derived from (WI-NRS or WP-NRS).

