### 5.5.2 Secondary Endpoints

The secondary endpoints follow two quite different analysis strategies.

The two continuous endpoints (all defined from Baseline to Week 12):

- Mean change in weekly mean Worst Pain Numeric Rating Score (WP-NRS) recorded in the patient's diary (Weekly mean WP-NRS is calculated as the average of WP-NRS values recorded in the patient's diary for 7 days prior to the in-clinic visits.)
- Change in Skindex-29 domains

will be analysed in an identical fashion to the primary endpoint described in Section 5.5.1, which includes one analysis on the FAS with imputation, and a further four sensitivity analyses, all without imputation.

The four binary endpoints (all defined from Baseline to Week 12):

- Percentage of patients obtaining a  $\geq 4$ -point improvement in weekly mean WI-NRS recorded in the patient's diary
- Percentage of patients obtaining a  $\geq 4$ -point improvement in weekly mean WP-NRS recorded in the patient's diary
- Percentage of patients obtaining a  $\geq 3$ -point improvement in weekly mean WI-NRS recorded in the patient's diary
- Percentage of patients obtaining a  $\geq 3$ -point improvement in weekly mean WP-NRS recorded in the patient's diary

will be analysed using the treatment policy strategy on the FAS in a logistic regression model with a factor for treatment, and covariates menopausal status at baseline, ICIQ-UI-SF score at baseline, as well as the baseline value of the scale the binary endpoint is derived from (WI-NRS or WP-NRS). The estimated log odds ratios between treatments at Week 12 will be reported, along with the 95% confidence interval. The logistic regression models will be carried out on worst case imputation data, where missing endpoint data is assumed to be no response.

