### 5.6 Changes and Clarifications to Analyses Planned in the Study Protocol

There are two changes to the sub-group analyses specified in section 9.4.6 in the protocol:

- The stratification by country will not be carried out as the study is carried in only one country
- Similarly, the stratification by site is deemed superfluous due to both the smaller sample size than expected, and possibly sites with very small sample sizes

In section 9.4.8 the exploratory endpoint burden living with VLS is only assessed at Screening and will only be listed, not described in summary tables.

Statistical within-treatment group pre-post testing was added to descriptive summary tables of selected endpoint as specified above.

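### SAP 5.4.1 and 5.5.2 disagree on how the responder models code ICIQ-UI-SF and baseline NRS, and no rule covers an arm with no responders

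*SAP*

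**What the plan says.** The four endpoints are improvements of at least 3 or at least 4 points in weekly mean WI-NRS and WP-NRS at Week 12, with missing values counted as non-response.

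- SAP 5.4.1 lists the effects as treatment, menopausal status, ICIQ-UI-SF score "and the baseline value for each scale the binary endpoint is derived from (WI-NRS or WP-NRS) as factors". It promises a log odds ratio with standard error and 95% confidence interval.
- SAP 5.5.2, for the same endpoints, specifies a logistic model "with a factor for treatment, and covariates menopausal status at baseline, ICIQ-UI-SF score at baseline", plus the baseline value of the scale.
- The multiple-imputation text in SAP 4.7.2 adjusts for menopausal status and "ICIQ-UI-SF score at baseline as factors, and the baseline value of the respective endpoint as a covariate", so there the two words carry different meanings within one sentence.
- SAP 4.3 reads "Similarly for the two binary secondary endpoints, which will be analyzed using a logistic regression at Week 12", although 5.5.2 and Table 5 list four such endpoints.
- Protocol 9.4.2.2 plans "logistic regression adjusting for respective NRS scores at baseline", with no menopausal or ICIQ-UI-SF term. SAP 5.6 opens its list of changes with "There are two changes to the sub-group analyses specified in section 9.4.6 in the protocol" and nowhere records the added terms.

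Neither document says what is reported if an arm has no responders or the likelihood has no finite maximum. The exact binomial tests in SAP 3.2.1 are within-arm and do not compare treatments.

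**The concern.** Calling a 0–21 score and a seven-day mean factors gives each distinct value its own parameter; calling them covariates gives each one slope. With 33 patients the first model is close to saturated and the second has five parameters, so the two sections describe different analyses.

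Choosing the second does not settle the matter. With an empty arm, the maximum-likelihood treatment odds ratio is infinite or zero and the promised standard error and interval do not exist.

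Four of the six listed secondary endpoints rest on this model, and SAP 2.4.1 calls their analysis confirmatory. Without a stated rule, an endpoint could end with no usable estimate, or a rescue method could be chosen after the data are seen.

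**Working it through.** **The plan's own figure.** Protocol 9.2 gives power only for the primary endpoint: "For a two-sided test with a 5% level of significance and an effect size of 1 standard deviation", 16 to 17 per arm, at least 78%. For a two-sample t-test the noncentrality is 1/√(1/16 + 1/17) = 2.87 on 31 df, giving 79.4%; 16 v 16 gives 78.1%. The figure is reproduced. No corresponding figure exists for the responder endpoints.

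**Columns under literal 5.4.1 coding.** ICIQ-UI-SF has 22 possible values. A complete seven-day WI-NRS mean of at least 4 runs from 28/7 to 70/7, which is 43 possible values. Simulated trials of 33 patients held about 12 ICIQ-UI-SF levels and 21 baseline levels: 1 intercept + 1 treatment + 1 menopausal + 11 + 20 = 34 columns. Across simulations the range was 30–38, and the treatment odds ratio was finite in 0.3–3.5% of trials.

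**Empty arm, exact.** With 17 on vehicle and 16 on cream, P(no responders) is (1 − p_V)^17 and (1 − p_C)^16. At 10/30%: 0.90^17 = 0.167 and 0.70^16 = 0.003, so P(either) = 1 − 0.833 × 0.997 = 17%. An arm in which everyone responds has the same effect and is included below.

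**Linear coding, simulated.** There were 1,000 trials per scenario (Monte Carlo SE at most 1.6 points). The odds ratio counts as lost only if separation or non-identification involves the treatment term. Baseline WI-NRS is a mean of seven integer scores, with person mean 6.5 and SD 1.7, restricted to at least 4. 63% have a non-zero ICIQ-UI-SF score (the incontinence prevalence cited in the protocol) and 75% are menopausal. Apart from the entry floor of 4 and the 63%, these settings and the response rates are assumptions.

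| Vehicle/cream rate, WI-NRS | Empty or full arm, exact | Empty or full arm, simulated | OR not finite, SAP terms linear | OR not finite, protocol model |
|---|---|---|---|---|
| 5/25% | 42% | 44% | 45% | 44% |
| 10/10% | 32% | 33% | 34% | 33% |
| 10/30% | 17% | 18% | 19% | 18% |
| 15/45% | 6% | 8% | 9% | 8% |
| 20/50% | 2% | 2.5% | 3% | 2.5% |
| 30/60% | 0.3% | 0.2% | 0.5% | 0.2% |

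The last two columns nearly coincide, so the added menopausal and ICIQ-UI-SF terms are not the cause; the empty arm is.

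**Pain endpoints.** Eligibility sets a floor for itch ("At least moderate itch defined as average WI-NRS ≥ 4 at the Baseline visit") and none for pain. A patient with baseline WP-NRS below 3 or 4 cannot improve by that much. With an assumed WP-NRS mean of 4–6 and SD 2.5, 51–89% of patients could respond at all. At 10/30, 20/50 and 30/60% among those able to respond, the odds ratio was not finite in 23–37%, 5–10% and 0.6–3% of trials (3-point endpoint) and in 30–46%, 7–20% and 1–7% (4-point endpoint).

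**What one such result looks like.** Take 0/17 on vehicle and 5/16 on cream. Fisher's exact p = C(16,5)/C(33,5) = 4368/237336 = 0.018; the opposite extreme is more probable and is not added. Ordinary maximum likelihood with treatment alone, stopped after 12 iterations, gives a log odds ratio near 12 with SE about 179 and Wald p = 0.94. Firth's method, which in this two-by-two case amounts to adding 0.5 to each cell, gives (5.5/11.5)/(0.5/17.5) = 16.7. In the simulations, Firth fits with the SAP's four terms converged to a finite estimate in at least 99.8% of trials in every scenario.

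**The case against.** The best reply is that this is loose drafting. Section 5.5 applies the methods endpoint by endpoint, so 5.5.2 should govern, and it says covariates. The SAP elsewhere calls two-level menopausal status a covariate. A programmer would notice a model with as many columns as patients, and SAP 5.7 defers technical detail to programming specifications that are not public. ICIQ-UI-SF as a factor might also mean incontinent or not, since a score of 1 or more indicates incontinence. All this makes the near-saturated model unlikely to survive to reporting. It does not reconcile the two sections, and the yes/no reading of ICIQ-UI-SF cannot explain baseline NRS as a factor.

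Second, the empty-arm risk depends wholly on assumed rates, and the protocol says no vehicle effect can be predicted. That stands: the risk is small at 20/50% and negligible at 30/60% for itch. At 15/45% the simulated empty-arm figure (8%) is also somewhat above the exact 6%.

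Third, an empty arm does not destroy all inference. For 0/17 v 5/16, the unadjusted likelihood-ratio p is 0.004 and the lower profile bound is 2.9. Response rates and bar charts would still be shown. This also stands, but the SAP specifies neither the test nor the bound.

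Finally, this is a 33-patient exploratory trial without multiplicity control, and a fallback sentence could replace Firth throughout. A pre-specified fallback would close the gap. Using one method for all four endpoints avoids a data-dependent switch.

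**Conclusion.** The concern holds. The contradiction between 5.4.1 and 5.5.2 is textual and needs no assumption. Read literally, 5.4.1 gives a model that almost never yields a treatment odds ratio. Under 5.5.2, the chance of losing the odds ratio for an itch endpoint runs from 0.5% to 45% over the assumed rates. It is driven almost entirely by an arm without responders and is generally higher for the pain endpoints. Those percentages rest on assumed response rates, baseline distributions and menopausal share. The absence of a rule does not.

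The matter should be fixed before unblinding. It concerns four secondary endpoints and leaves the primary MMRM untouched. The count of two in 4.3 and the omission from 5.6 are minor documentation gaps.

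**What to change.** - In SAP 5.4.1, state that ICIQ-UI-SF score and baseline NRS enter as continuous linear covariates, as in 5.5.2, with menopausal status as a two-level class variable. Make the ICIQ-UI-SF wording in 4.7.2 equally explicit.
- Pre-specify Firth penalised likelihood with profile-likelihood intervals for all four responder endpoints.
- Report the difference in response rates with an exact or score interval beside each odds ratio.
- Keep the menopausal and ICIQ-UI-SF terms if wanted, but record them in 5.6 as a change from the protocol model. Correct the count in 4.3 to four.

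The cost is SAP text and the FIRTH option in PROC LOGISTIC. The odds ratio is shrunk slightly towards 1 in ordinary data. With an empty arm the penalty is what makes it finite, which is a further reason to show the raw rates alongside.
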